Effective date: 2022-03-21 13:08

[figure not shown]
Effective

Version: 3.0

SYNOPSIS	
	
randomized and dispensed the investigational product, and will be analyzed according to the randomization scheme. The ITT population will be the primary population used for efficacy analysis.
 
 • The per protocol (PP) population is a subset of the ITT subjects who complete the Month 1 visit and have no protocol deviations that are considered to have a substantial impact on the primary efficacy outcome. • The safety population includes all subjects who were administered the study product, and will be analyzed according to as-treated principle. All safety data will be summarized descriptively based on the safety population. 
CCI

Sample Size:	
Interim Analysis:	Not applicable.

2022-03-21 13:08

[figure not shown]
Effective date:

CLINICAL STUDY SCHEMATIC AND FLOW CHART**Table 1 Clinical Study Schematic***Effective*

Version: 3.0

2022-03-21 13:08

Effective date:

Figure 1 Study Flow Chart**Effective**

Version: 3.0

GALDERMA EST. 1981	Title 43QM2106 Clinical Study Protocol – QM1114 – GL	Doc id MA-49290
------------------------------	--	---------------------------

SCHEDULE OF ASSESSMENTS

Table 2 Schedule of Assessments

Visit	Visit 1	Visit 2	Visit 3	Visit 4	Visit 5	Visit 6	Visit 7	Visit 8	Visit 9	Visits 10-14	Visit 15
1 month = 4 weeks All visit windows are calculated from Baseline/Day 0		Day 0 Baseline ¹	Day 1	Day 2	Day 3	Day 4	Month 1	Month 3	Month 6	Months 7-11	Month 12/ EOS/ET ²
Window	(≤ 2 weeks of Visit 2)						(± 5 days)	(± 5 days)	(± 5 days)	(± 5 days)	(± 5 days)
Informed Consent	X										
Demographic Data ³	X										
Medical History	X										
Previous Medication/Procedures ⁴	X										
Urine Pregnancy Test ⁵	X	X ⁷									X
Focused Physical Examination ⁶	X	X ⁷	X	X	X	X	X	X	X	X	X
Vital Signs ⁸	X	X ¹⁰	X	X	X	X	X	X	X	X	X
Inclusion/Exclusion Criteria	X	X ⁷									
Photography		X ⁷	X	X	X	X	X	X	X	X	X
CCI											
Blood sample for serum antibody testing		X ⁷					X		X		
Randomization		X ⁷									
Treatment		X									
Dispense Subject Diary Card		X									
Collect Subject Diary Card							X				
Adverse Events	X	X ¹⁰	X	X	X	X	X	X	X	X	X
Concomitant Medication/Procedures	X	X ¹⁰	X	X	X	X	X	X	X	X	X
SUBJECT ASSESSMENTS											
CCI											
GAIS			X	X	X	X	X	X	X	X	X
INVESTIGATOR ASSESSEMENTS											
CCI											

CONFIDENTIAL
Page 18 of 86

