6.1.7.3 Treatment Regimen

Each subject will receive a single treatment with QM1114-DP or placebo at the baseline visit.

The treatments investigated in this study are:

- 50 U of QM1114-DP (0.5 mL total injection volume/0.1 mL per injection point)
- Placebo

CCI

 EST. 1981	Title 43QM2106 Clinical Study Protocol – QM1114 – GL	Doc id MA-49290
---	--	---------------------------

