1.5.1 Adverse events

Adverse events (AEs) are to be monitored throughout the course of the study. All AEs reported will be coded using the Medical Dictionary for Regulatory Activities (MedDRA, Version 25.0 – March 2022 or higher) and classified by MedDRA preferred term (PT) and system organ class (SOC). AEs will be defined as treatment-emergent adverse events (TEAEs) if the AE had an onset time greater than or equal to the time of study treatment. The study period for the purpose of AE collection is defined as the period from the signing of a study specific informed consent to study exit.

A two-point scale (“Yes” or “No” response) will be used for the causality assessments. The Treating Investigator should be asked to indicate a response to each of the following questions in the electronic Case Report Form (eCRF):

- “Do you consider that there is a reasonable possibility that the event may have been caused by the study product?”
- “Do you consider that there is a reasonable possibility that the event may have been caused by the study product injection procedure?”

If either of these questions is answered with a ‘Yes’, the AE will be considered related.

All AEs will be monitored by the Sponsor to determine if they meet the criteria of remote spread of effect of the toxin or hypersensitivity, which will be included as an AE endpoint. A list of preferred terms for these types of events will be analyzed to determine if there is a plausible possibility that they represent remote spread of toxin or hypersensitivity. The Sponsor will consider variables including alternative etiology (medical history, concomitant medications, or diagnosis which could account for the symptoms), location of QM1114-DP administration, and temporal relationship to

QM1114-DP administration in order to perform the analysis. Sponsor determination will be cross-referenced with Investigator-reported potential remote spread of the toxin or hypersensitivity AEs. Before unblinding the subject data, and as a part of preparations for the database lock, the study team will review and adjudicate all AEs to create a finalized list of remote spread of toxin or toxin hypersensitivity events for the analysis.

Refer to Galderma Work Instruction QMS-13549 effective 16MAR2022 and to the Data Management Plan V1.0 for more details on this process.

AE endpoints include incidence and severity of TEAEs.

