2.5.2 Adverse events

All AE data will be summarized by treatment group. Missing dates will be imputed as described below. AEs will be summarized by SOC and PT. AEs occurring before treatment will be presented in listings only. The MedDRA version used for the coding will be noted as a footnote in the tables and listings. In general, percentages for the number of subjects will be calculated using the number of subjects in the safety population for the denominator.

A summary of all AEs will be provided, which will include:

- number (%) of subjects who did not have an AE
- number (%) of subjects with at least one TEAE and number of events
- number (%) of subjects and events with at least one TEAE related to study product or injection procedure and number of events
- number (%) of subjects and events with at least one TEAE not related to study product or injection procedure and number of events
- number (%) of subjects and events with at least one TEAE leading to discontinuation and number of events
- number (%) of subjects and events with at least one serious TEAE and number of events
- number (%) of subjects and events with at least one serious related TEAE and number of events
- number (%) of subjects and events with at least one AE that meets the criteria of remote spread of effect of toxin or hypersensitivity and number of events

Summaries of TEAEs (including the total number of events, number and percentage of subjects) will be displayed by treatment group according to the following:

- All TEAEs by SOC and PT
- Treatment emergent SAE by SOC, PT, maximum intensity (mild, moderate, severe), and causality
- Related TEAEs by SOC and PT, and maximum intensity (mild, moderate, severe)
- Unrelated TEAEs by SOC and PT, and maximum intensity (mild, moderate, severe)
- TEAEs leading to discontinuation by SOC and PT, and maximum intensity (mild, moderate, severe)
- TEAEs by SOC, PT, and action taken (none, medical treatment, non-pharmacological treatment, subject withdrawn)
- TEAEs that meet the criteria of remote spread of effect of toxin or hypersensitivity by SOC, PT, and maximum intensity (See [Section 2.5.2.2](#))

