2.5.3 Anti-drug Antibodies (ADA)

Sampling for antibody testing will be conducted at baseline Day 0, Month 1, and Month 6. The following ADA categories will be determined based on the confirmatory assay results:

- ADA positive at any point in time, baseline or post-baseline.

- ADA positive post-baseline and positive at baseline.
- ADA positive post-baseline and not detected at baseline (treatment-induced ADA).
- ADA not detected post-baseline and positive at baseline.
- Treatment-boosted ADA, defined as a baseline positive ADA titer that was boosted to a 4-fold or higher level (greater than the analytical variance of the assay) from baseline following drug administration.
- Treatment-emergent ADA positive, defined as either treatment-induced ADA or treatment-boosted ADA.
- Persistently positive ADA, defined as having at least 2 post-baseline ADA positive measurements with at least 16 weeks (112 days) between the first and last positive measurement or an ADA positive result at the last available assessment. The category may include subject meeting these criteria who are ADA positive at baseline.
- Transiently positive ADA, defined as having at least one post-baseline ADA positive measurement and not fulfilling the conditions for persistently positive. The category may include subjects meeting these criteria who are ADA positive at baseline.
- nAb positive at any point in time, baseline or post-baseline.

The number and percentage of subjects who develop detectable ADA within each ADA response category listed above will be summarized by treatment group, including ADA prevalence and ADA incidence (proportion of ADA-positive and treatment-emergent ADA-positive subjects, respectively, in the ADA Evaluatable population). The titer values of ADA-positive subjects will be summarized descriptively (using n, min, Q1, median, Q3, max) by treatment group and visit. The kinetics of ADA development will be assessed by summarizing the number and percentage of ADA-positive subjects at each visit by treatment group.

The impact of ADA on safety data (inclusive but not limited to) any AEs, any SAEs, and any adverse events of special interest (AESIs) will be evaluated by summary statistics based on ADA status.

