ADA safety tables will be summarized by treatment group and will include: (1) the number of subjects who had at least 1 AE in any category will be summarized by ADA category (ADA positive, ADA negative, treatment-emergent ADA positive, and nAb positive); (2) a summary of subjects with injection site reactions or hypersensitivity events by ADA status will be presented; (3) a data listing of adverse events among subjects who developed anti-drug antibodies.

A line plot of ADA positivity in each treatment group will be presented by visit. A box plot of titer values in each treatment group will be presented by visit.

If there are more than 20 subjects in the QM1114-DP treatment group who are treatment-emergent ADA positive, a summary of the duration and onset of ADA may be generated as well as the impact of ADA on the primary efficacy endpoint.

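### The ADA safety tables in SAP 2.5.3 do not order adverse event onset against antibody detection, so early reactions to the Day 0 injection appear as events in subjects first found antibody-positive weeks or months later

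*SAP*

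**What the plan says.** On sampling, SAP 2.5.3 states: "Sampling for antibody testing will be conducted at baseline Day 0, Month 1, and Month 6". The baseline sample is drawn before treatment (Protocol Table 2).

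On classification, the first category listed in SAP 2.5.3 is "ADA positive at any point in time, baseline or post-baseline". Treatment-emergent positive combines treatment-induced ADA (not detected at baseline, positive later) with treatment-boosted ADA (a baseline titer raised at least 4-fold).

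On the safety tables, SAP 2.5.3 plans three outputs by treatment group:
- Table (1) counts subjects with at least one AE by four categories: ADA positive, ADA negative, treatment-emergent ADA positive and nAb positive.
- For table (2), "a summary of subjects with injection site reactions or hypersensitivity events by ADA status will be presented". Which status is meant is not stated.
- Output (3) lists the AEs of subjects who developed ADA.

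On the event window, SAP 1.5.1 collects AEs over "the period from the signing of a study specific informed consent to study exit", and SAP 2.5.2 adds that "AEs occurring before treatment will be presented in listings only". The tabulated events therefore run from treatment to exit.

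On treatment, Protocol 6.1.7.3 states: "Each subject will receive a single treatment with QM1114-DP or placebo at the baseline visit".

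**The concern.** The tables are meant to show whether antibodies influence safety, and for that the antibody should be known to precede the event. A treatment-induced antibody can be known only from a sample at Month 1 or later, whereas reactions to the injection can start on Day 0. Table (1) assigns each subject a status from all three samples and then counts events from the whole post-treatment period, so the classification can postdate the event.

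A reader of the clinical study report who saw reactions in the treatment-emergent positive row could take them as a possible consequence of the antibody when they came before any evidence of it. The groups are likely to be small, so one such case would move a percentage visibly. The comparison in which the antibody status is known to come before the reaction, namely baseline status against reactions to the study injection, is not specified. It is of interest here because the inclusion criteria (Protocol 5.2.1) require repeated prior BoNT-A treatment.

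**Working it through.** The SAP gives no expected event count, ADA incidence or power figure for these tables, so there is no planned figure to reproduce. The check is of the timeline.

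**Inputs.** Protocol Table 2 gives "1 month = 4 weeks All visit windows are calculated from Baseline/Day 0", with windows of ±5 days from Month 1 onwards. Visits with an AE enquiry from Day 0 are Days 0, 1, 2, 3, 4, then Months 1, 3, 6, 7, 8, 9, 10, 11 and 12, which is 14 visits.

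**Sample days.**
- First post-treatment sample: 1 × 28 = Day 28, window 23-33.
- Last sample: 6 × 28 = Day 168, window 163-173.
- End of follow-up: 12 × 28 = Day 336.

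**Follow-up that precedes first post-treatment detection.**

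| First positive at | Days before detection | Share of 336 days | AE visits before detection |
|---|---|---|---|
| Month 1 | 28 (23-33) | 28/336 = 8.3% (6.8-9.8%) | 5 of 14 (Days 0-4) |
| Month 6 | 168 (163-173) | 168/336 = 50% | 7 of 14 (the above plus Months 1 and 3) |

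With in-window sampling, a reaction that begins before Day 23 precedes every possible post-treatment detection. It still counts under treatment-emergent positive if the Month 1 or Month 6 sample makes the subject so.

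**Which subjects are affected.**
- Treatment-induced: yes, for any event before the first positive sample.
- Treatment-boosted: only as to the boost, because antibody was already present at baseline.
- Positive at baseline: not affected; the antibody was found before the injection.

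The ADA-positive row of table (1) contains all of these together.

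**Illustration under assumed values (none is in the documents).** Suppose ADA has no effect, every reaction starts before Day 23, each subject has reaction probability p, and k subjects are treatment-induced. The chance that the table shows at least one reaction in that group is 1 − (1 − p)^k.

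| k | p = 5% | p = 10% | p = 20% |
|---|---|---|---|
| 1 | 5% | 10% | 20% |
| 3 | 14% | 27% | 49% |
| 5 | 23% | 41% | 67% |
| 10 | 40% | 65% | 89% |

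Under these assumptions every such reaction would fall before first detection, and none on or after it.

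**The case against.** The strongest reply is that little depends on these tables. They are descriptive and untested, and they touch neither the primary endpoint nor the main TEAE tables. Event order can be checked for the subjects concerned: output (3) lists the AEs of subjects who developed ADA, SAP 2.1.1 puts the relative study day on listings, and ADA positivity is shown by visit. All of that stands and limits the consequence. It does not change what tables (1) and (2) display.

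Four stronger readings are tempting, and the documents do not support them.

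- A reader might infer that no treatment-induced antibody can be found before Day 28. The window allows Day 23, and SAP 2.1.1 tabulates by recorded visit even when a visit is out of window. Actual sample dates must be used.
- A reader might infer that the antibody was absent when an early reaction occurred. Detection is interval-censored: antibody found at Month 1 may have formed at any time since Day 0, and antibody first found at Month 6 at any time since the last negative sample. The point concerns detection only.
- A reader might infer that a baseline comparison is ruled out. The four categories belong to table (1). Table (2) leaves the status open, and SAP 2.5.3 already defines two categories of baseline-positive subjects. The comparison is unspecified, not excluded.
- A reader might infer that subjects who leave before Month 1 are counted as ADA negative. The SAP does not say so. Safety analyses use observed cases (SAP 2.5), and SAP 2.5.3 names an ADA-evaluable population for prevalence and incidence. That population is not among the three in SAP 2.2, and ADA negative is not among the listed categories. This is a gap in definition, not evidence of misclassification.

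**Conclusion.** The point holds for subjects first positive after treatment and, as to the boost, for treatment-boosted subjects. For them, table (1) places events that began before the qualifying sample in the treatment-emergent positive row, and nothing in SAP 2.5.3 separates those events. It does not hold for baseline-positive subjects, although the ADA-positive row does not let a reader tell the two apart. Table (2) may share the problem, depending on which status is used.

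In calendar terms the misordered period is 8.3% of follow-up for first detection at Month 1 and 50% for first detection at Month 6. In both cases it includes the injection day and the four daily visits after it. The size in events is unknown, because the documents as available give neither ADA incidence nor reaction rates; the illustration rests on assumed values. The consequence is a safety summary that could be misread, not a threat to the trial's main conclusions.

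**What to change.** Amend SAP 2.5.3 as follows.

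1. Tabulate injection site reactions and hypersensitivity by baseline ADA status (positive, not detected) within treatment group, and name this as the status used in table (2).
2. For treatment-emergent positive subjects, show AEs in two rows: onset before, and onset on or after, the first positive sample (for boosted subjects, the first sample meeting the boost definition). Use actual sample dates.
3. State that detection is interval-censored, so the earlier row does not prove that antibody was absent.
4. Keep the planned ever-positive table as supplementary.

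The earlier events should be shown, not dropped. Counting only events after detection would remove the early reaction period from post-treatment positives while negatives still counted from Day 0. After a single injection that creates the opposite bias, and reporting exposure time would not repair it because early reaction risk is not constant.

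The cost is SAP wording and a few table shells. Sample results, sample dates and AE dates are already collected. The downside is a few more rows with small counts in a descriptive summary.

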2.5.4 Physical examinations and vital signs

The number and percentage of subjects with normal/abnormal results in physical examination will be presented by visit and treatment. A shift table will be created to present any change from baseline in normal/abnormal results in physical examination across the study visits for each treatment group.

Vital signs and the changes from baseline will be summarized by treatment and visit using descriptive statistics.

[figure not shown]
2.5.5 Urine pregnancy test

A data listing will be provided to summarize the results of the urine pregnancy tests.

2.6 Interim Analysis

Not applicable.

CCI

3 Reference List

1. Bohdana Ratitch, et al. "Combining Analysis Results from Multiply Imputed Categorical Data", 2013, PharmaSUG Proceedings, Paper SP-03
2. Medical Dictionary for Regulatory Activities Terminology (MedDRA), Version 25.0, MedDRA MSSO, March 2022.
3. WHO Drug Dictionary, March 2022 – Version B3, Uppsala Monitoring Centre (UMC) Box-1051, SE-751 40 Uppsala, Sweden.
4. Center for Drug Evaluation and Research "E9(R1) Statistical Principles for Clinical Trials: Addendum: Estimands." *U.S. Food and Drug Administration*, FDA, May 2021.

4 Appendix A: Schedule of Assessments

[figure not shown]
Visit	Visit 1	Visit 2	Visit 3	Visit 4	Visit 5	Visit 6	Visit 7	Visit 8	Visit 9	Visits 10-14	Visit 15
1 month -4 weeks All visit windows are calculated from Baseline/Day 0	Screening ¹	Day 0 Baseline ¹	Day 1	Day 2	Day 3	Day 4	Month 1	Month 3	Month 6	Months 7-11	Month 12/ EOS/ET ²
Window	(≤ 2 weeks of Visit 2)						(± 5 days)	(± 5 days)	(± 5 days)	(± 5 days)	(± 5 days)
Informed Consent	X										
Demographic Data	X										
Medical History	X										
Previous Medication/Procedures ⁴	X										
Urine Pregnancy Test ⁵	X	X ⁷									X
Focused Physical Examination ⁶	X	X ⁷	X	X	X	X	X	X	X	X	X
Vital Signs ⁸	X	X ⁷	X	X	X	X	X	X	X	X	X
Inclusion/Exclusion Criteria	X	X ⁷									
Pharmacotherapy		X ⁷	X	X	X	X	X	X	X	X	X
CCI											
Blood sample for serum antibody testing		X ⁷					X		X		
Randomization		X ⁷									
Treatment		X									
Dispense Subject Diary Card		X									
Collect Subject Diary Card							X				
Adverse Events	X	X ¹⁰	X	X	X	X	X	X	X	X	X
Concomitant Medication/Procedures	X	X ¹⁰	X	X	X	X	X	X	X	X	X
SUBJECT ASSESSMENTS											
CCI											
GAIS			X	X	X	X	X	X	X	X	X
INVESTIGATOR ASSESSMENTS											
CCI											

Abbreviations

EOS – End of Study, ET – Early Termination **CCI**GAIS – Global Aesthetic Improvement Scale **CCI**

1. Screening and baseline visits may be performed on the same day. If performed on the same day, study activities should only be completed once (i.e., UPT, subject and investigator GL severity assessments, focused physical exam, vital signs, and inclusion/exclusion criteria review).
2. If the subject withdraws before the final visit the assessments at Month 12/EOS/ET should be completed, if possible.
3. Includes date of birth, gender, race, ethnicity, height, weight, Fitzpatrick skin type.
4. For previous toxin treatments, capture, brand, area(s) treated, and date(s) on the previous medications/procedures form.
5. Females of childbearing potential.
6. Post-baseline, events suggestive of remote spread of toxin are also considered while doing clinical evaluations based on the subject's symptoms and signs. Directed questioning and examination will then be performed as appropriate.
7. Performed pre-treatment.
8. Vital signs include blood pressure, heart rate and respiratory rate. Vital signs are taken seated, after approximately 10 min rest.
9. Only at select sites.
10. Performed pre- and post-treatment.
11. Subject will make his/her assessment independently of the investigator's assessment.
12. Performed at month 9 only.
13. Part 1 to be completed post-treatment at baseline (Visit 2) and Part 2 to be completed at Month 1 (Visit 7).

CCI

CCI
